CLINICAL STUDY PROTOCOL

Study Title: **An Open-Label, Non-Controlled Study to Evaluate Outcomes of Pulsed Electromagnetic Field (PEMF) Therapy in Subjects with Various Pain Etiologies**

Protocol Number: RBI.2015.005

Version: B

Phase: Post-Market

Sponsor: Regenesis Biomedical, Inc.
[name]
[name]

Medical Contact: [name]
Vice President, Clinical Business and Education
Regenesis Biomedical, Inc.

Final Approval Date: 18 January 2017

PROTOCOL SIGNATURE PAGE – SPONSOR

Study Title: **An Open-Label, Non-Controlled Study to Evaluate Outcomes of Pulsed Electromagnetic Field (PEMF) Therapy in Subjects with Various Pain Etiologies**

Protocol Number: RBI.2015.005

Version: B

The undersigned acknowledges that he/she has received and read Protocol RBI.2015.005, Version B, dated 18 January 2017.

Sponsor Representatives	Signature	Date
[name] Vice President, Clinical Business and Education		
[name] Director Clinical Research		

PROTOCOL SIGNATURE PAGE – Principal Investigator

Study Title: **An Open-Label, Non-Controlled Study to Evaluate Outcomes of Pulsed Electromagnetic Field (PEMF) Therapy in Subjects with Various Pain Etiologies**

Protocol Number: RBI.2015.005

Version: B

The undersigned acknowledges that he/she has received and read Protocol RBI.2015.005, Version B, dated 18 January 2017.

Principal Investigator	Signature	Date

DOCUMENT REVISION HISTORY		
	Date	Summary of changes
Version A	01/11/2016	Original document
Version B	1/18/2017	Updated to include the Numeric Pain Rating Scale (NPRS), Clinical Global Impression – Global Improvement (CGI-I) Scale, Patient Global Impression of Change (PGIC) and 3-Month follow-up and signature line for [name].

Study Synopsis

Study Title	An Open-Label, Non-Controlled Study to Evaluate Outcomes of Pulsed Electromagnetic Field (PEMF) Therapy in Subjects with Various Pain Etiologies
Protocol Number	RBI.2015.005
Name of Study Device	Provant [®] Therapy System
Phase of Development	Post-Market
Objective	To obtain data on the safety and effectiveness of PEMF treatment in patients with various pain etiologies. Data from enrolled patients will contribute to a patient registry on the post-market use of Provant.
Number of Subjects	Up to 300 subjects will be enrolled.

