All concomitant drug and non-drug treatments as well as the frequency of administration and indication for the treatment will be recorded in the subject's chart. Based on the subject's pain etiology, the investigator may disallow certain concomitant medications in order to accurately assess the effect of Provant therapy. Opioid or other pain drug therapies may be reduced or discontinued during the treatment period of the study as directed by the subject's treating physician.

It is important to record the reason why each analgesic medication is being taken by the subject, specifically analgesics taken for treatment of pain/edema. In this context, "analgesic medications" refers to medications prescribed and administered for the treatment of pain, and includes but is not limited to opioids, nonsteroidal anti-inflammatory agents, anti-depressants and muscle relaxants.

Prohibited Medications/Treatments

The following medications and therapeutics are prohibited throughout the study:

- Systemic steroids or topical steroids on the treatment location
- Transcutaneous electrical neurostimulators (TENS units)
- Implanted neurostimulators
- Local injections
- Intrathecal infusion
- Acupuncture
- Surgery

V. WITHDRAWAL PROCEDURES

If a subject or the prescriber decides to discontinue the subject's treatment with the device, efforts will be made to perform all assessments scheduled for the End of Treatment Visit prior to subject withdrawal.

VI. STATISTICAL CONSIDERATIONS

The statistical analysis of the study is described in detail in a separate version-controlled Statistical Analysis Plan (SAP). However, the statistical methodology described in this section of the protocol will be the basis for the detailed SAP.

Where not otherwise specified, the last pre-treatment observation will be used as baseline for calculating post-treatment changes from baseline. All confidence intervals will use a significance level of 5%.

A. Study Populations

Safety summaries will be conducted on all subjects who undergo treatment.

The effectiveness summaries will also be conducted on all subjects who undergo treatment. Subjects that do not attend the End of Treatment Visit will be excluded from the End of Treatment analyses. Subjects who complete the End of Treatment Visit will be assessed for efficacy regardless of the number of days of treatment received. No imputation of data will occur.

B. Efficacy Data Summaries

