Demographic and subject characteristics will be summarized using descriptive statistics. Assessments that are measured on a continuous scale will be summarized descriptively using the mean, standard deviation, median, minimum, and maximum value by time. Variables that are measured on a categorical scale will be summarized as a proportion of the population.

The change from baseline will be summarized for effectiveness outcome assessments in common between subjects/sites and 95% confidence intervals constructed.

Adverse events will be summarized using MedDRA categories and by severity and relationship. Concomitant medications will be summarized by WHODrug categories.

C. Adverse Events

All adverse events will be coded according to Medical Dictionary for Regulatory Activities (MedDRA). Safety assessments will include treatment-emergent adverse events (TEAEs; adverse events that occur in subjects who undergo treatment). Subjects with TEAEs will be summarized with frequencies and percentages by system organ class and preferred term, severity, and relationship to treatment for each treatment group. Treatment-related adverse events will be defined as adverse events with investigator assessment of related or possibly related. In summaries of TEAEs by severity and relationship to study device, subjects reporting multiple episodes will be counted once under the worst severity and the strongest relationship, respectively. Serious Adverse Events will also be presented by relationship to treatment.

The number of subjects with at least one adverse event will be tabulated. The number of adverse events will also be tabulated. The number of subjects and the number of adverse events will be tabulated by severity and relationship.

D. Sample Size

This is an open-label, non-controlled study with no formal hypothesis testing planned. It is anticipated that up to 300 subjects will be enrolled in this study. Data from this study will be included in a patient registry. The statistical analysis plan for the patient registry will fully describe the methods used to evaluate data from this study.

VII. INFORMED CONSENT

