## **4. STUDY OVERVIEW**

### **4.1. Study Design**

This is an open-label, non-controlled trial in subjects with various pain etiologies at multiple centers in the US. Up to 200 subjects will be enrolled. Eligible subjects will include those  $\geq 22$  years of age that have been deemed appropriate for treatment with Provant by the study investigator (prescriber). Subjects will treat based on the treatment prescribed (location, frequency, duration) by the study investigator. Data from assessments administered as part of standard of practice will be obtained at baseline and, at a minimum, at the end of treatment. If the investigator administers additional assessments during the course of treatment, the data will be collected. Safety will be assessed during office visits and through review of AE reports and concomitant treatments and medications. All concomitant drug or non-drug treatments used during the study will be recorded.

Subjects will be instructed in the use of the device and will self-treat as prescribed by the study investigator. As part of the investigator's standard of practice, subjects may be provided with a patient reported outcome form(s) for capturing their daily pain scores, which may include a 10 point numerical pain score scale, or other patient-reported outcomes related to the pain etiology. Subjects will document outcomes as instructed by the site at the Enrollment Visit.

After up to 20 weeks of treatment, the subject will return to the clinic for a final assessment. Adverse events and changes in concomitant medications will be collected.

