#### **4.5. Interim Analysis**

An administrative extract of the data on September 2, 2016 will be used to tabulate the data for the post-operative patients. This tabulation is being prepared for a regulatory filing and does not constitute a formal analysis.

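### The NPRS, CGI-I, PGIC and 3-month call were added after data collection had apparently begun, but the summaries ignore protocol version and the final pain score has no item or visit window

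*Protocol*

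**What the plan says.** The protocol's revision history lists Version A, dated 01/11/2016, as "Original document". Version B, dated 1/18/2017, is described as "Updated to include the Numeric Pain Rating Scale (NPRS), Clinical Global Impression – Global Improvement (CGI-I) Scale", together with "Patient Global Impression of Change (PGIC) and 3-Month follow-up".

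SAP 4.5 states: "An administrative extract of the data on September 2, 2016 will be used to tabulate the data for the post-operative patients".

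On the analysis set, Protocol VI.A states: "The effectiveness summaries will also be conducted on all subjects who undergo treatment". It excludes from the End of Treatment analyses only those who miss that visit, and imputes nothing. Protocol VI.B has continuous measures "summarized descriptively using the mean, standard deviation, median, minimum, and maximum value by time" and categorical measures as a proportion of the population. The synopsis instead limits each efficacy summary to subjects who completed that evaluation at that time point.

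SAP 6 defines one combined ITT/Safety population. The SAP 7 displays split by reason for enrollment, and SAP 7.4 by condition treated. The pain rows of the Level 2 display, and SAP 10.3, take each subject's last recorded value. SAP 5 ends at the End of Treatment Visit. The SAP does not name the NPRS, CGI-I or PGIC.

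**The concern.** In an uncontrolled study the evidence is the course of pain from baseline, through treatment, to 3 months after it. That course can be read only if each row refers to a defined time point and successive rows refer to the same people. If required measures start partway through enrollment and the tables ignore this, two things can go wrong.

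- A row for the last pain score can stand for the end of treatment in earlier subjects and for three months off treatment in later ones.
- Baseline, End of Treatment and 3-month means can come from different sets of subjects. A difference between rows may then reflect who was enrolled when, and not whether relief lasted.

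Protocol I gives the purpose as confirming earlier findings of pain relief, and VI.B attaches 95% confidence intervals to the changes. The tables will therefore be read as evidence even though no hypothesis is tested.

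**Working it through.** The plan gives no figure to reproduce: Protocol VI.D says up to 300 subjects, and SAP 4.3 says its 200 has no formal basis. The check is of dates and definitions.

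**1. Timeline.** The Version B entry is month-first, so Version A is read as 11 January 2016. A day-first reading (1 November 2016) would fall after the planned extract.
- Version A to Version B: 373 days.
- Extract to Version B: 28 + 31 + 30 + 31 + 18 = 138 days.
- Maximum follow-up in SAP 4.4: 20 × 7 = 140 days, including screening. A subject consented by 2 September 2016 would finish by 20 January 2017, two days after Version B.
- If the protocol's 20 weeks of treatment follow up to 14 days of screening, the limit is 154 days, or 3 February 2017, 16 days after Version B.

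On either reading, nearly all subjects in the extract would have completed treatment, or all but its last days, before the added measures were required.

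**2. What each row can contain.**

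| Row | Subjects before Version B | Subjects under Version B |
|---|---|---|
| CGI-I, PGIC | None, unless still on study at the change | Interim and End of Treatment |
| 3-month NPRS | None, unless called after the change | Phone call |
| Last pain score on study (SAP 7, 10.3) | Last on-treatment or end-of-treatment score | The same, or the 3-month phone NPRS |
| Pain change from baseline | Within subject, if a baseline exists | Within subject |

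Only the pain rows can combine eras. Standard-of-practice and edema measures also span both versions, but the amendment did not change them.

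**3. Denominator.** For CGI-I and PGIC, VI.B read with VI.A gives all treated subjects, less those who missed the End of Treatment Visit. An earlier subject who attended that visit but was never offered the scale would still count. The synopsis would not count that subject.

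**4. Illustration only.** Let f be the share of earlier subjects. Assume the same End of Treatment mean E in both eras, and that every later subject supplies a 3-month score averaging E + d. Then

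last-score mean = f·E + (1 − f)(E + d) = E + (1 − f)d.

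With d = 1 point and f = 0.1, 0.3 or 0.5, the row lies 0.90, 0.70 or 0.50 from the End of Treatment mean and 0.10, 0.30 or 0.50 from the 3-month mean. With d = 0.5 these distances halve. The row then estimates neither time point. None of f, d or the completeness of the calls is given in the documents.

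**5. Precision cost of separating versions.** Assume an SD of change of 2.5. The 95% half-width is 1.96 × 2.5/√n: 0.28 at n = 300, and 0.30, 0.34 or 0.40 at n = 270, 210 or 150 (f = 0.1, 0.3 or 0.5).

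**The case against.** The strongest reply is that the plan already limits the damage. The synopsis counts only subjects who completed the evaluation, nothing is imputed, change from baseline is within subject, VI.B confines it to assessments in common, and SAP 7 requires each table to show its N. This stands for CGI-I, PGIC and the 3-month NPRS. A reader might infer that every row mixes eras, but those rows cannot. The rule does not, however, make successive rows refer to the same subjects, and it sets no window for the last score.

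A second reply is that the SAP has no 3-month visit, puts participation at up to 20 weeks, and uses a 7-day average at visits, so a phone NPRS might never reach its last-score row. That is fair: the mixing is permitted, not shown to be intended. But Protocol Appendix A makes the call part of the schedule, and the SAP neither includes nor excludes it.

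A reader might also infer that the pain item changed with the amendment, because SAP 4.1 refers to a form "which may include a 10 point numerical pain score scale". That phrase describes an optional daily form. The SAP's own baseline item (3.2.1) runs from 0 to 10, which is 11 points, and Version A's text is not available. The unstated recall period at baseline, against the 7-day average later, lies within the SAP and is separate from the amendment.

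Finally, a reader might want a percentage of NPRS values lacking a baseline. This needs accrual dates and a rule for moving ongoing subjects to Version B, and the documents give neither. If ongoing subjects were not moved, the share is 0%.

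**Conclusion.** The concern holds in a limited form. The documents support three statements:

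- The added measures apparently post-date the start of data collection. This is inferred from the extract date, since no first-enrollment date is given.
- Protocol version appears nowhere in the analysis sets, displays or subgroups.
- Read literally, the last-score rule gives a time point that depends on when the subject was enrolled.

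For CGI-I, PGIC and the 3-month NPRS the defect is selected coverage, with an unclear denominator for the two global scales. For pain it is possible mixing of time points and of subjects across rows. The size cannot be computed because the number of subjects enrolled before Version B is not stated; the figures in step 4 only show how the mechanism works. The point is more than missing detail, because a same-subject comparison is clearly better and costs little. It should be corrected before the tables are produced.

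**What to change.** Revise SAP 6, 7 and 10 to match protocol Version B:

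1. Limit the final pain score to on-treatment and End of Treatment values, and report the 3-month NPRS in its own row.
2. Show End of Treatment and 3-month NPRS change side by side for the same subjects, namely those with a baseline score on the same 0-10 item. State which item feeds each pain row.
3. Derive a protocol-version flag from the enrollment date, show it in Table 14.1.1, and present pain change by version as well as overall.
4. Use subjects assessed on the scale as the CGI-I and PGIC denominator, leaving out the CGI-I code for not assessed, and align Protocol VI.B with the synopsis.

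Pain scores from before Version B need not be discarded if the 0-10 item is the same. The cost is SAP wording, one derived flag, and a smaller N with wider intervals in the same-subject and by-version rows.

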APPENDIX A - TIME AND EVENTS SCHEDULE

Period	Screening Visit	Enrollment (Baseline) Visit ¹	Treatment Period	Interim Visits	End of Treatment Visit	Follow-up Phone Call
Study Day	-14 to 0	0	As Prescribed	As Prescribed	As Prescribed	3 months post-treatment
Informed Consent	X					
Demographic Information	X					
Medical/Surgical History	X					
Urine Pregnancy Test ²	X					
Height and Weight	X				X ⁷	
Inclusion/Exclusion Criteria	X	X				
Efficacy Outcomes Assessments (Including NPRS, CGI-I and PGIC)		X ³		X ³	X ³	X ³
Study Device Training		X ⁴				
Dispense Study Device		X				
Distribute Diary Collection Tool(s)		X ⁵				
Study Device Treatment			X ⁶			
Assess Adverse Events and Concomitant Medications	X ⁸	X		X	X	
Assess Subject Adherence to Treatment				X	X	
Collect Diary Collection Tool(s)				X	X	
Return Study Device and Unused DACs					X ⁹	

1. The Screening Visit and the Enrollment Visit may occur on the same day in which case none of the screening tests need to be repeated.
2. Urine pregnancy test will be performed on women of child-bearing potential.
3. The CGI-I and PGIC will not be conducted at the Enrollment (Baseline) Visit. Only the NPRS will be captured at the Follow-up phone call.
4. Introduction to and training on the study device will be completed during the Enrollment Visit.
5. Distribution of a diary collection tool will occur if the investigator decides to use this as a means for capturing patient reported outcomes. Completion of the forms will occur as instructed by the investigative site, as applicable.
6. The subject will self-administer treatments as prescribed by the investigator.
7. Collect only weight at End of Treatment Visit.
8. Assessment of adverse events will be conducted after the signing of the Informed Consent.
9. At the End of Treatment Visit subjects will return the study device and all unused Disposable Applicator Covers (DACs).

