	
scores, which may include a 11 point numerical pain score scale, or other patient-reported outcomes related to the pain etiology. Subjects will document outcomes as instructed by the site at the Enrollment Visit.
 
The site will contact the subject via telephone or the subject will come for an interim visit at regular intervals (to be determined by the investigator based on treatment regimen and standard of practice) to assess subject adherence to treatment, completion of patient reported outcomes, NPRS, CGI-I, PGIC and any safety concerns and/or changes in concomitant treatments/medications.
 
After up to 20 weeks of treatment, the subject will return to the clinic for a final assessment that will include the NPRS, CGI-I and PGIC. Adverse events and changes in concomitant medications will be collected.
 
Three months post-treatment, a follow-up phone call will be made to collect the NPRS.

Study Device	
The study device is the Provant[®] Therapy System which delivers Pulsed Electromagnetic Field (PEMF) energy therapy. Each device will be identified by a unique serial number.

Study Sample	
The anticipated enrollment in this study is up to 300 subjects. The study will be conducted at multiple (up to 25) sites.

Outcome Measures	
Outcome measures will be assessed in order to allow for characterization of the response to PEMF therapy.
 
Efficacy Assessments
 
Outcome measures of response to treatment with Provant will be determined based on the pain and/or edema being treated. The initial evaluations will include treatment of post-surgical hand edema, arterial insufficiency, diabetic peripheral neuropathy, abdominoplasty and other plastic surgeries, post-hernia surgical pain, and pelvic pain. All outcome measures used as part of the standard of practice regimen will be non-invasive assessments e.g., pain scores, SF-36, ankle-foot scales, oxygen perfusion (MOXY), and diaries with some subjects. Protocol required assessments will include the NPRS, CGI-I and PGIC.
 
Subject adherence (compliance with the prescribed treatment regimen) will be assessed verbally during follow-up and upon completion of the treatment period. A subject with complete adherence will be expected to have a usage meter reading of 1.0 for every hour that the subject treated.

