Outcome measures of response to treatment with Provant will be determined based on the location of the subject's treatment area. Protocol required assessments will include baseline and interim / end of treatment visit and 3-month follow-up (post-treatment) pain scores using an 11-point numeric pain rating scale (NPRS), and a Clinical Global Impression – Global Improvement (CGI-I) Scale and a Patient Global Impression of Change (PGIC) Scale. All outcome measures administered as part of non-invasive standard of practice assessments will be collected, e.g., pain scores, SF-36, ankle-foot scales, oxygen perfusion (MOXY), and diaries with some subjects.

2. Safety Assessments

Safety will be assessed through review of AE reports and concomitant treatments and medications. All concomitant drug or non-drug treatments used will be recorded. Safety outcomes will be assessed at office visits as defined by the treatment regimen.

IV. STUDY PROCEDURES

The study procedures are summarized in the Schedule of Events (Appendix A) and described immediately following:

A. Visit 1 – Screening Visit (Day -14 to 0)

The Screening Visit will take place no more than 14 days prior to the Enrollment Visit. If a successfully screened subject falls out of the 14-day limit, the subject will require another screening to participate. The following procedures will be performed:

1. Informed consent review and signature.
2. Review Inclusion and Exclusion criteria.
3. Collect subject demography data (including age, weight, height, gender, and race/ethnicity).
4. Collect Medical and Surgical History.
5. Review and record all concomitant medications.
6. Perform a urine pregnancy test for females of child bearing potential.
7. If the subject meets the eligibility criteria, continue on to the Enrollment Visit.

If subject does not require any washout for prohibited medications or procedures, the Screening Visit and the Enrollment Visit can be conducted concurrently.

B. Visit 2 – Enrollment Visit (Day 0)

The following procedures will be performed:

1. Review Inclusion/Exclusion criteria (if Screening/Enrollment visits not combined).

2. Review and record any changes in medical history and study eligibility criteria since screening (if Screening/Enrollment visits not combined).
3. Review and record adverse events (if Screening/Enrollment visits not combined).
4. Review and record any changes in concomitant medications (if Screening/Enrollment visits not combined).

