5. Conduct baseline efficacy assessments.

Response to treatment with Provant will be determined based on the location of the subject's treatment area. Assessments will include the NPRS and non-invasive assessments part of the investigator's standard of practice e.g., pain scores, SF-36, ankle-foot scales, oxygen perfusion (MOXY), and diaries with some subjects.

6. If the subject continues to meet eligibility criteria, enroll subject, and dispense study device.
7. Introduce and train the subject on the use of the Provant Therapy System, including instructions for proper positioning and operation of the device.
8. If applicable, distribute a patient diary and instruct the subject on how to complete. Examples of diary collection tools are provided in Appendix B.

During this visit, eligible subjects will receive a Provant device and up to 120 Disposable Applicator Covers (packs of 30, depending on the anticipated treatment duration) and the subject will be instructed to administer treatment as prescribed by the investigator.

C. Treatment Period

Treatment may be self-administered by the subject, or with the assistance of a family member or caregiver. Subjects will assume a comfortable position and place the treatment applicator pad of the Provant device centering the applicator pad on the treatment location as instructed by the investigator. Treatment will be administered for 30 consecutive minutes.

Subjects will be asked to complete the patient reported outcome form(s) as instructed (as applicable).

D. Interim Visits

Subjects will be required to return to the clinic during the course of treatment as instructed by the investigator. Telephone follow-ups may also be performed with each subject as determined by the investigator. At these interim visits, the following will be collected if assessed:

1. Review and record adverse events
2. Review and record all concomitant medications
3. Assess adherence to Provant treatment regimen

4. Assess completion of the patient reported outcome form(s), as applicable
5. Conduct efficacy assessments:

Response to treatment with Provant will be determined based on the location of the subject's treatment area. Assessments will include the NPRS, CGI-I, PGIC and non-invasive assessments part of the Investigators standard of practice e.g., pain scores, SF-36, ankle-foot scales, oxygen perfusion (MOXY), and diaries with some subjects.

E. End of Treatment Visit

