Subjects will return to the clinic after completion of treatment as required by the study investigator. At this visit, the following procedures will be performed:

1. Collect subject's weight
2. Review and record adverse events
3. Review and record all concomitant medications
4. Conduct efficacy assessments:

Response to treatment with Provant will be determined based on the location of the subject's treatment area. Assessments will include the NPRS, CGI-I, PGIC and non-invasive assessments part of the Investigators standard of practice e.g., pain scores, SF-36, ankle-foot scales, oxygen perfusion (MOXY), and diaries with some subjects.

5. Return of study device and unused DACs
6. Return of the patient reported outcome form(s), as applicable. Examples of diary collection tools are provided in Appendix B.

F. Post-treatment Phone Call

Three months after the End of Treatment Visit, subjects will be contacted via telephone and asked to rate their pain using the NPRS.

G. Treatment adherence/study compliance

Subject adherence (compliance with the prescribed treatment regimen) will be assessed during interim visits and upon completion of the treatment period by the research staff reading and recording the number displayed on the study device usage meter. The usage meter will read 0.0 when dispensed. A subject with complete adherence will be expected to have a usage meter reading of 1.0 for each hour of treatment.

Subjects will be instructed to return any unused DACs at the End of Treatment visit. Compliance will be assessed by counting the number of returned, unused DACs, and subtracting this from the total number of DACs dispensed (120). As each treatment session requires one new DAC, compliance can be calculated based on the number of returned DACs relative to the prescribed regimen.

H. Protocol Adherence

If protocol modifications are necessary, all alterations that are not solely of an administrative nature require a formal protocol amendment.

If an investigator has deviated from the protocol in order to eliminate an immediate hazard to subjects or for other inevitable medical reasons, the investigator shall document all such deviations, including the reasons thereof, and immediately submit the documentation to the sponsor and to the IRB if required.

I. Concomitant Medications

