An adverse event is defined as follows: Any untoward medical occurrence in a patient or clinical investigation patient administered a medical device treatment which does not necessarily have to have a causal relationship with this treatment. An AE can therefore be any unfavorable and unintended sign (including an abnormal laboratory finding), symptom, or disease temporally associated with the use of study device treatment, whether or not considered related to the study device.

All AEs occurring after signing of the consent form will be recorded. AEs arising subsequent to the time of initiation of first treatment with study device will be considered treatment emergent AEs.

At each contact with the subject, the investigator or designee must seek information on AEs by non-leading specific questioning and, as appropriate, by examination. All observed or volunteered AEs, regardless of suspected causal relationship to study device, must be recorded in the patient's chart.

Any events involving illnesses or injuries with onset during the study or any events involving exacerbations of pre-existing illnesses should be recorded. All clearly related signs and symptoms should be grouped together and recorded as a single diagnosis in the patient's chart. A pre-existing condition must not be reported as an AE unless the condition worsens during the trial.

Each AE will be independently judged by the investigator in terms of causality. The following definitions will be used for these causality assessments.

- | | |
|--------------------------|--|
| Related: | This causal relationship is assigned when the AE: 
 • starts a reasonable time after study device administration, • cannot be reasonably explained by the subject's clinical state. |
| Possibly Related: | This causal relationship is assigned when the AE: 
 • starts a reasonable time after study device administration, but • could have been produced by the subject's clinical state or other modes of therapy administered to the subject. |
| Unrelated: | This causal relationship is assigned when the AE: 
 • is definitely not associated with the study device administered and is readily explained by other events or diagnoses. |

Each AE will also be independently judged by the investigator in terms of severity. The following definitions will be used for these severity assessments.

- | | |
|------------------|--|

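### Protocol X.A requires AE questioning at every contact, but the 3-month follow-up call is scheduled without it, and no end is set for the treatment-emergent window

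*Protocol*

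**What the plan says.** **Questioning and recording rules.** Protocol X.A states: "At each contact with the subject, the investigator or designee must seek information on AEs by non-leading specific questioning". It makes no exception for telephone contacts. It also states "All AEs occurring after signing of the consent form will be recorded", with no closing date, and treats events that begin after first device use as treatment-emergent. On existing conditions it says: "A pre-existing condition must not be reported as an AE unless the condition worsens during the trial". X.B lists increased pain among the anticipated effects.

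**The call.** IV.F reads: "Three months after the End of Treatment Visit, subjects will be contacted via telephone and asked to rate their pain using the NPRS". The synopsis agrees: "Three months post-treatment, a follow-up phone call will be made to collect the NPRS". Appendix A marks the AE and concomitant-medication row at Screening, Enrollment, Interim and End of Treatment, and leaves it empty for the call. Footnote 3, attached to the efficacy row, says "Only the NPRS will be captured at the Follow-up phone call". III.L.2 adds: "Safety outcomes will be assessed at office visits as defined by the treatment regimen".

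**SAP.** The section 5 schedule stops at End of Treatment. Section 4.4 describes follow-up of up to 20 weeks. Section 11.1.2 bases every AE summary on treatment-emergent events and gives no cut-off.

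**The concern.** Safety is a stated objective, and the AE tables report the percentage of subjects with each event. Such a percentage can be interpreted only if all subjects in the denominator were asked over the same period. The call is the only scheduled contact after the device is returned. Whether AEs are sought there depends on which part of the protocol a site works from, and up to 25 sites may not choose alike.

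Pain is where this matters most. The call takes a pain score, so it can reveal worsening, and worsening can be a reportable AE. The two global impression scales are not taken at the call. If AEs are not asked about either, a higher score may be the only trace of a deterioration, and it would not reach the AE tables unless it was volunteered or recognised by staff. No text says how such a score is to be handled.

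**Working it through.** The plan has no figure to reproduce: there is no formal hypothesis test or sample-size calculation, and no AE rate is given. The check is mainly a comparison of texts.

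**1. Is the call a contact under X.A?** Yes. IV.F says subjects are contacted by telephone. The synopsis already has telephone contacts during treatment cover safety concerns, so the use of a telephone does not take a contact outside X.A.

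**2. Does the schedule ask for AEs there?** No. The AE cell is blank and IV.F lists no AE step, whereas IV.D and IV.E name AE review for the interim and End of Treatment visits. This holds without footnote 3, which may mean only that the CGI-I and PGIC are dropped at the call.

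**3. Does any text close the window?** None found. III.C and X.A fix its opening at first treatment. SAP 11.1.1 deals with missing onset dates and sets no last date. SAP 4.4 gives 30 days of further follow-up for AEs already ongoing at study completion, but does not say whether completion means End of Treatment or the call. Protocol X.C refers to a final follow-up visit, which Appendix A does not list under that name.

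**4. How different are the two observation periods?** Take 3 months as 91 days, and let T be the days from first treatment to End of Treatment. The share of time after End of Treatment is 91/(T + 91).

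- 20 weeks of treatment (synopsis maximum), T = 140: 91/231 = 39.4%
- All 120 applicator covers (the maximum dispensed under IV.B) used once daily, T = 120: 91/211 = 43.1%
- All 120 covers used twice daily, T = 60: 91/151 = 60.3%

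These are shares of calendar time, nearly all of it off the device. They are not shares of AEs.

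**5. What would a mixture do to a percentage?** Let f be the fraction of subjects at sites that ask at the call. Let q be the proportion of subjects who would be added to an AE row only because they were asked. To first order, assuming q is similar across sites, the reported percentage rises by f × q, which is 300 × f × q subjects at the planned maximum of 300. Neither f nor q is in the documents. Assuming q from 1% to 10%:

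- f = 0: 0 subjects
- f = 0.5: 300 × 0.5 × 0.01 = 1.5 to 300 × 0.5 × 0.10 = 15 subjects
- f = 1: 300 × 0.01 = 3 to 300 × 0.10 = 30 subjects

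This shows scale under an assumption and is not an estimate.

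**The case against.** The strongest reply is that a blank cell forbids nothing. X.A is mandatory and covers every contact, so the two texts can be read together and sites should ask at the call. That is a fair reading of intent. It does not remove the problem, because staff who work from the schedule and IV.F get no prompt to ask.

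Several other replies stand and limit the point:

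- **AE collection at the call is not prohibited.** A reader might infer a ban from footnote 3. The documents do not support that, since the footnote concerns efficacy scales.
- **Late events are not simply lost.** X.A and III.C require observed, reported or volunteered events to be recorded, and a worse score taken by staff is arguably observed. Serious events and unanticipated device effects are reportable within 24 hours of knowledge, whatever the visit. What is exposed is mainly new, non-serious events that surface only when asked about.
- **A higher score at the call is not automatically an AE.** The natural comparator in X.A is the subject's condition at entry. A subject who goes from 7 to 3 on treatment and then to 6 has lost benefit but is still better than at baseline.
- **No large distortion of the AE rates can be shown.** Any such contrast would rest on assumed rates of contact, worsening and on-treatment events.

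The SAP also looks older than Protocol Version B: it plans 200 subjects rather than 300 and omits the CGI-I, PGIC and call. Its silence may reflect that. Protocol VI.D also defers full methods to a registry plan that is not available here. Neither point resolves the disagreement within the protocol.

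**Conclusion.** The inconsistency is real and lies within the current protocol; the available SAP text does not settle it. AE questioning after End of Treatment may differ between sites, so AE percentages could combine subjects questioned to End of Treatment with subjects questioned about 3 months longer. The likely effect is confined to new non-serious events that are neither volunteered nor observed. Its size cannot be derived from the documents. The 3-to-30-subject range at full enrollment assumes that every site asks and that 1% to 10% of subjects are added by asking.

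No hypothesis test is affected, and AE collection up to End of Treatment is unaffected. This is a correction that should be made because it is cheap and makes ascertainment uniform. It does not invalidate the safety analysis.

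**What to change.** **Appendix A:** mark the AE and concomitant-medication row under the Follow-up Phone Call.

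**IV.F:** add a review of AEs and concomitant medications since the End of Treatment Visit. State that the investigator judges a higher NPRS score to be an AE when pain is worse than at baseline, and not merely because on-treatment benefit has been lost.

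**SAP:** add the call to the section 5 schedule, end the AE window at the call, and tabulate AEs with onset up to End of Treatment separately from those with later onset.

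**Cost:** two short questions in a call already planned, one eCRF page, and a split of the AE tables. A few more late, unrelated events will be recorded, and with no control group they are hard to attribute. The onset split keeps them apart from the on-treatment figure.

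**Alternative:** if the sponsor wants the call to take the NPRS only, limit the X.A questioning rule to contacts through the End of Treatment Visit and state the same cut-off for the AE tables in the SAP. This also makes the rule uniform, at the price of no active AE questioning after the device is returned.
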